5.2 Toxities and Dosing Delays/Dose Modifications

Patients who receive radiation treatment on this protocol will be evaluable for toxicity. Toxicity will be assessed according to the NCI Common Terminology Criteria for Adverse Events (CTCAE), version 4.0. If these toxicities occur **during treatment**, then RT will be held until resolution: Grade ≥ 3 ascites, change in ALBI score by 0.5, Child Pugh score greater than or equal to 2.

5.3 Duration of Therapy

Therapy would typically continue until delivery of the intended number of fractions. If liver function declines after the first 3/5 of treatments and does not recover sufficiently for additional therapy, then treatment will also be considered complete after 3 fractions (see above for definition).

Treatment will also be complete if a patient voluntarily withdraws from treatment or changes in the patient's condition render the patient unacceptable for further treatment in the judgment of the investigator.

5.4 Off Treatment Criteria

Patients will be removed from protocol therapy when any of the criteria listed in Section 5.3 apply, with documentation provided. All patients who discontinue treatment should comply with protocol specific follow-up procedures as outlined in Section 6.3. The only exception to this requirement is when a subject withdraws consent for all study procedures, loses the ability to consent freely, or is removed from follow up per the investigator's discretion, as in Section 5.6.

5.5 Duration of Follow-Up

Patients will be followed for 2 years after completion of treatment or until death, whichever occurs first. If patients progress outside of the treated tumor, they will only be followed for survival, without mandated visits with study personnel, as long as they are being seen routinely every 3-6 months by an oncologist or hepatologist. These clinic notes can be requested for study purposes, and tumor measurements tracked from clinical scans.

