5.6 Off Study Criteria

Patients can be taken off study at any time at their own request, or they may be withdrawn at the discretion of the investigator for safety, behavioral or administrative reasons. Patients will be considered off study after completion of protocol treatment and follow-up criteria.

The reason(s) for discontinuation from study will be documented and may include:

5.6.1 For patients planning to receive ICG testing in lieu of ALBI, patients will be removed if

- they are unable to complete the pre-treatment and post- 3 fraction IC Green tests, as these are necessary for dose adjustment.
- 5.6.2 Patients will be removed if they are unable to receive RT treatments.
- 5.6.3 Patients may be removed from study at any time by patient request.
- 5.6.4 Patients who enroll in subsequent liver radiation therapeutic trials are considered off study for initial enrollment. Local control for all treated lesions will be tracked on the follow up schedule for the subsequent enrollment to avoid duplicate procedures.
- 5.6.5 Patients who have progression of the treated lesion will be followed for survival and toxicity only.
- 5.6.6 Patients who go on to receive additional liver-directed to the treated lesion or systemic therapy (non-radiation therapy, on or off protocol) will be followed for survival only.
- 5.6.7 Patients can be removed from study if they are unable to comply with protocol requirements.
- 5.6.8 Patients can be removed from study if the treating physician judges that continuation on the study would not be in their best interest.

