8.0 ADVERSE EVENTS

8.1 Adverse Event Reporting Requirements

Data on adverse events will be collected from the time of the first radiation treatment through 2 years after completion of radiation. Serious Adverse Events (SAEs) will continue to be followed until:

- Resolution or the symptoms or signs that constitute the serious adverse event return to baseline;
- There is satisfactory explanation other than the study treatment for the changes observed; or
- Death.

The definitions of AEs and SAEs are given below.

Any medical condition or laboratory abnormality with an onset date before initial study treatment is considered to be pre-existing in nature. Any known pre-existing conditions that are ongoing at time of study entry should be considered medical history rather than an AE.

In addition to new events, any increase in the frequency or severity (i.e., toxicity grade) of a pre-existing condition that occurs after the patient begins treatment is also considered an adverse event if it meets the definitions below.

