11.3 Data Analysis Plans

Primary Aims: The first primary aim is feasibility which is defined as the ability to successfully deliver the full treatment including all adaptations and in particular the perfusion based planning and replanning. In the simplest analyses, feasibility will simply be summarized as the proportion of patients for whom the intended treatment was feasible. The reasons for lack of feasibility for any patients will be investigated individually.

The primary efficacy endpoint is local control, measured as the time to progression of the treated lesion. Patients with no evidence of local progression at the time of data analysis will be censored at the last date on which they were evaluated for local progression. Local progression will be summarized with Kaplan-Meier curves. The estimated rate of local control at 6, 12, 18 and 24 months will be estimated and reported with 95% confidence intervals. Cox regression models will be used to assess the relation between the hazard of local progression and tumor dose and other covariates.

The primary toxicity endpoint is defined as a change in Child Pugh score of greater than or equal to 2 within 6 months of SBRT. Secondary toxicity endpoints include changes in ALBI scores and grade 3 toxicities described in section 8. RILD is a rare but serious side effect that will also be summarized if it occurs. Logistic regression models will be used to estimate the association between baseline (primarily baseline liver function such as CP score and mean liver dose and other dose metrics such as D700) and mid-treatment variables (e.g. change in ICGR15) and the probability of toxicity. We will include interactions between dose and baseline liver function as there is some evidence that patients with worse liver function are more sensitive to radiation than patients with better baseline liver function.

Secondary Aims: The relation between various biomarkers and treatment efficacy will be assessed by including the biomarkers as covariates in Cox regression models for local progression. The relation between biomarkers and toxicity will be assessed in logistic regression models for the binary or ordinal toxicity outcomes and linear regression models for continuous measures of toxicity or liver function such as ICGR15 or ALBI.

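### Survival-only follow-up after out-of-field progression or further therapy leaves the 6-month Child-Pugh endpoint, and in part 1-year local control, without assured ascertainment

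*Combined protocol and SAP*

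**What the plan says.** Three provisions set what is collected after a post-treatment event.

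- **Progression outside the treated tumor (5.5):** "If patients progress outside of the treated tumor, they will only be followed for survival, without mandated visits with study personnel". This applies only "as long as they are being seen routinely every 3-6 months by an oncologist or hepatologist". The section then adds: "These clinic notes can be requested for study purposes, and tumor measurements tracked from clinical scans".
- **Systemic therapy, or more liver-directed therapy to the treated lesion (5.6.6):** patients who go on to "systemic therapy (non-radiation therapy, on or off protocol) will be followed for survival only", and the same holds for further treatment of the lesion. Clinic notes and scans are not mentioned.
- **Progression of the treated lesion (5.6.5):** "Patients who have progression of the treated lesion will be followed for survival and toxicity only".

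Section 8.1 makes no exception for any of these groups: "Data on adverse events will be collected from the time of the first radiation treatment through 2 years after completion of radiation".

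Section 11.3 defines the primary toxicity endpoint as a "change in Child Pugh score of greater than or equal to 2 within 6 months of SBRT". It analyses local control as time to progression of the treated lesion, censored at the last local evaluation. Under section 11.2 the treatment is promising enough for a phase II trial if toxicity is at most 25% and 1-year local control is at least 80%.

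**The concern.** All three triggers for survival-only follow-up arise after treatment and can come before month 6 or month 12. They are also plausibly linked to the outcomes: patients who progress elsewhere or need more therapy may differ in liver reserve and in local tumor behaviour. Missing values in that group would not be missing at random.

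The provisions also disagree. Toxicity is still followed after local progression (5.6.5) but not after the other triggers, while 8.1 promises adverse-event data on everyone for 2 years. Section 8.1 would not rescue the endpoint in any case. Under 8.2.1 a laboratory abnormality is an adverse event only if it causes symptoms or needs therapy, and 5.1.1.2 obtains Child-Pugh from bloodwork plus a physical exam.

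Nothing later in the plan repairs this. Sections 5.7 and 11.2 do not require a 6-month Child-Pugh or a 1-year scan for a patient to be evaluable, and 6.3 does not treat missed visits as deviations. At stake are both halves of the go/no-go rule and the event count behind the toxicity model.

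**Working it through.** **1. The plan's own figure.** Section 11.2 expects 80 × 0.20 = 16 toxicity events, which reproduces. It assumes the 6-month outcome is known for all 80.

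**2. How many could be affected.** The documents give no figure for this trial. The nearest is in 1.1.2.1: about 50% failure elsewhere in the liver after RFA, in a review with a 3-year horizon. Assuming a constant hazard and a 3-year reading:

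- by 6 months: 1 − 0.5^(1/6) = 10.9%, or 0.109 × 80 = 8.7 patients
- by 12 months: 1 − 0.5^(1/3) = 20.6%

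This covers only the out-of-field route and comes from a different treatment, so I use an assumed range of 5–30% below.

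**3. Bounds on toxicity.** Let d be the share without a 6-month Child-Pugh result, with 20% toxicity among those observed. The lower bound is 0.20(1 − d) and the upper bound is 0.20(1 − d) + d.

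| d | Unobserved of 80 | Expected recorded events | Lower | Upper |
|---|---|---|---|---|
| 0% | 0 | 16.0 | 20% | 20% |
| 5% | 4 | 15.2 | 19% | 24% |
| 10% | 8 | 14.4 | 18% | 28% |
| 20% | 16 | 12.8 | 16% | 36% |
| 30% | 24 | 11.2 | 14% | 44% |

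The upper bound exceeds 25% when 0.20 + 0.80d > 0.25, so d > 6.25%, or more than 5 of 80. If toxicity among the unobserved is p, the true rate exceeds 25% when d > 0.05/(p − 0.20). That is d > 16.7% at p = 50% and d > 25% at p = 40%.

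**4. Direction for toxicity.** It depends on a rule that 11.3 does not give. Take 80 patients, a true rate of 30%, 16 truncated before 6 months, and half of their events falling after truncation (all assumed).

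- *Equal risk.* The other 64 have 64 × 0.30 = 19.2 events. The 16 have 4.8, of which 2.4 are recorded.
  - Truncated patients counted as non-events: 21.6/80 = 27.0%.
  - Only those without a recorded event dropped: 21.6/66.4 = 32.5%.
  - All truncated patients dropped: 19.2/64 = 30.0%.
- *Double risk.* The risk in the others is 0.30/(0.8 + 0.2 × 2) = 0.25, giving 16.0 events. The 16 have 8.0, of which 4.0 are recorded. The same three rules give 20/80 = 25.0%, 20/68 = 29.4% and 16/64 = 25.0%.

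The same data can therefore read below, at or above the truth.

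**5. Local control.** Assume an exponential model with 85% 1-year control in patients who stay. A share d is censored at 6 months and then has k times the hazard. True control is S₆[(1 − d)S₆ + d·S₆^k], with S₆ = √0.85 = 0.922.

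- d = 20%, k = 2 to 4: 83.7% to 81.3%
- d = 30%, k = 2 to 4: 83.0% to 79.5%
- every censored patient progresses: 0.85 × 0.8 = 68.0%, or 0.85 × 0.7 = 59.5%

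With the 97% reported for the preceding study (1.1.2.3), S₆ = 0.985. Then d = 30% and k = 4 give 0.985 × (0.7 × 0.985 + 0.3 × 0.941) = 95.7%.

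**The case against.** A reader might infer that both endpoints simply go unobserved once a patient progresses elsewhere. The documents do not say that. Section 5.5 has tumor measurements tracked from clinical scans, 7.1.4 does not count progression elsewhere as a local failure, and 11.3 censors at the last local evaluation, not at out-of-field progression. If the scans are tracked as stated, local control continues for these patients. For toxicity, 2.3.1.2 describes the decompensation measures as laboratory values already collected in standard care, and 6.3 accepts records from local physicians, so the data may well exist.

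A reader might also infer that the results are certain to look too favourable. For toxicity, step 4 shows that this depends on an unstated missing-data rule. For local control it requires a higher local hazard in the censored patients, which is plausible but not documented. If control is near 97%, the 80% threshold is not in play under the hazard multiples tried.

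Finally, stopping lesion assessment after further therapy to that lesion is a defensible estimand choice, since it avoids crediting SBRT with a later treatment. The trial is also a pilot seeking preliminary estimates.

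All of this limits the claim without removing it. Retrieval of clinic notes is optional, with no Child-Pugh items or time points named. Section 5.6.6 has no fallback. The estimand argument does not apply to a 6-month safety endpoint that 5.6.5 preserves after local progression, and a deliberate choice for local control should be written down.

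**Conclusion.** The point holds as a gap in assured ascertainment. That the sections disagree, and that 11.3 lacks a rule for a missing 6-month Child-Pugh result, is clear from the text. The consequence is less certain: I hold with moderate confidence that the loss is informative, and its size cannot be derived from the documents.

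Toxicity is the more exposed endpoint, having the weaker fallback and the smaller margin. Between the expected 20% and the 25% limit there is room for only 5 unobserved patients in the worst case, against about 9 by 6 months if the RFA figure carried over and none of their records were retrieved. Local control crosses 80% only at the extreme of the hazard multiples tried (30% censored with 4 times the hazard, starting from 85%), or under worst-case imputation. This should be fixed before the go/no-go rule is applied, but it does not show that either rate will be misjudged.

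**What to change.** **Sections 5.5 and 5.6.6.** Whatever the out-of-field progression or later therapy, require retrieval from routine clinic records of Child-Pugh components and adverse events through 6 months after RT, and of treated-lesion status from clinical scans through 12 months. Align 8.1 with these sections.

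**Section 11.3, toxicity.** Analyse all treated patients. State the rule for a missing 6-month Child-Pugh and for death before 6 months, and report best- and worst-case bounds.

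**Section 11.3, local control.** State that assessment does not end at out-of-field progression. State how systemic therapy and further therapy to the treated lesion are handled (censored or not), and report the alternative as a sensitivity analysis.

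**Cost.** Protocol wording and chart retrieval. Patients under 5.5 are already expected to be seen every 3–6 months; for 5.6.6 patients the work depends on what routine records exist. No treatment changes. The drawback is that some later toxicity will partly reflect progression or new therapy, so events should be reported with their timing relative to those changes.

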5.6 Off Study Criteria

Patients can be taken off study at any time at their own request, or they may be withdrawn at the discretion of the investigator for safety, behavioral or administrative reasons. Patients will be considered off study after completion of protocol treatment and follow-up criteria.

The reason(s) for discontinuation from study will be documented and may include:

5.6.1 For patients planning to receive ICG testing in lieu of ALBI, patients will be removed if

- they are unable to complete the pre-treatment and post- 3 fraction IC Green tests, as these are necessary for dose adjustment.
- 5.6.2 Patients will be removed if they are unable to receive RT treatments.
- 5.6.3 Patients may be removed from study at any time by patient request.
- 5.6.4 Patients who enroll in subsequent liver radiation therapeutic trials are considered off study for initial enrollment. Local control for all treated lesions will be tracked on the follow up schedule for the subsequent enrollment to avoid duplicate procedures.
- 5.6.5 Patients who have progression of the treated lesion will be followed for survival and toxicity only.
- 5.6.6 Patients who go on to receive additional liver-directed to the treated lesion or systemic therapy (non-radiation therapy, on or off protocol) will be followed for survival only.
- 5.6.7 Patients can be removed from study if they are unable to comply with protocol requirements.
- 5.6.8 Patients can be removed from study if the treating physician judges that continuation on the study would not be in their best interest.

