function¹⁹. Insertion of a treatment break did not compromise tumor control. Indeed, 1 year local control for the first 76 patients was 97%, comparable to any other prospective or retrospective report. Patients with very poor liver function (Child Pugh B and even C) were treated safely on trial, suggesting that modifying radiation dose part-way through treatment successfully avoided what would have been severe toxicity. Our initial analysis of the first 20 patients evaluable on the study showed that we need to begin adapting treatment prior to the first 3/5 of radiation delivery. We plan to accrue an additional 40 patients to examine the feasibility of up front individualization in addition to mid treatment adaptation to minimize toxicity and maintain excellent local control. We have demonstrated that patients with good liver function and small tumors (<3.5 cm) have excellent local control and very low rates of toxicity. The current protocol looks at adapting therapy for patients with good liver function (CPA to B7) but larger tumors where more liver parenchyma would receive radiation thereby increasing the risk of toxicity and those with poor liver function (CPB8 and above) who at baseline are at increased risk of liver decompensation post treatment. Our interim analysis has revealed that a combination of albumin and bilirubin, called ALBI, which is an accurate predictor of survival for patients with HCC with liver dysfunction³⁶, is as or more useful than ICG in estimating liver function and predicting future toxicity. Thus, either ICG or ALBI can be used in this trial.

1.1.4.1 Adjusting spatial RT distribution based on regional liver function as assessed by perfusion MRI. This protocol builds on over 25 years of experience with high dose liver RT, and in particular adaptive RT aimed at adjusting the global radiation dose based on a patient's measured sensitivity to treatment. The next leap forward is to use functional imaging to spare highly functional portions of the liver. We have previously demonstrated that dynamic contrast-enhanced (DCE or perfusion) MRI correlates with global liver function as measured by ICG, and that regionally, function declines as a function of delivered radiation dose.²⁹ This and, potentially, other advanced MRI techniques, provides the opportunity to sculpt dose away from high-functioning parts of the liver to improve the safety of treatment.

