5.1.1.2 Baseline bloodwork and physical exam to obtain ALBI and Child Pugh score

5.1.1.3 Regional functional assessment with perfusion MRI

MRIs will be obtained by trained personnel in the Department of Radiation Oncology at the University of Michigan.

5.1.1.3.1 Evaluations will occur within 4 weeks prior to the start of RT, at approximately 4-6 weeks after the completion of the first 3/5 of planned treatments, and approximately 1-3 months after RT is completed.

5.1.1.3.2 For patients scheduled to have perfusion MRI for other reasons (including prior or subsequent enrollment in this or other protocols), every effort will be made to use results for both purposes, to avoid duplication, including extending windows by an extra 4 weeks in each direction.

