5.7 Patient Replacement

Patients who do not complete the pre-treatment and post 3/5 of treatment IC Green tests or bloodwork to evaluate ALBI score, along with the initial 3/5 of treatment are considered non-evaluable and will be replaced until a total of 80 evaluable patients is reached (80 patients).

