6.4 Time and Events Table

	Pre-Rx Eval ¹	Initial RT Phase	Active Treatment	
			Evaluation Period Approximately 4-6 Weeks after Initial RT Phase	Final RT phase ⁵
History, Physical Exam, Performance Status, QOL⁸	X	PS	QOL	PS
Weight	X	Once	X	Once
CBC/Platelets	X		X	
AST, ALT, Alk Phos, Bilirubin	X		X	
BUN/Creatinine	X		X	
INR	X		X	
AFP (for HCC)	X		X	
Toxicity Notation	X	Once		Once
MELD/CTP assessment	X		X	
IC-Green⁶	X		X ⁴	
Simulation	X		X	
Perfusion MRI⁹	X		X	
Tumor biopsy⁷	X			
Diagnostic CT or MRI of liver	X ²			
Chest imaging with x-ray or CT	X ³			
Plasma and serum	X		X	
Radiation Treatment (RT)		X		X

¹ From 30 days prior to signed ICF, through treatment start.

² From 90 days prior to signed ICF, through treatment start.

³ Within 1 year prior to enrollment

⁴ If a patient does not initially qualify for the final RT phase, he/she will undergo repeat IC-Green in approximately 4 weeks as a second attempt.

⁵ Patients who do not qualify for the final RT phase will not undergo any of the treatment or testing associated with that phase. The final day of the initial RT phase will be counted as the last day of treatment, and the follow up calendar will be initiated.

⁶ For patients indicated to receive IC-Green from the treating physician. If the patient was previously enrolled on any trial utilizing IC-Green (including this one), then an evaluation of IC-Green retention performed for the other trial may be used as the pre-treatment assessment for this enrollment, as long as it is within 30 days prior to initiation of this new course of RT.

⁷ Biopsy only performed if patient consents

⁸ QOL will consist of the Functional Assessment of Cancer Therapy-Hepatobiliary (FACT-HEP) version 4. As patients can be seen in a variety of clinics, and occasionally do not follow a standard clinic schedule, missed QOLs will not be reported as a protocol deviation.

⁹ Description of Perfusion MRI protocol in the appendix.

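### Section 5.6.1 takes ICG-path patients off study for a missed mid-treatment ICG test after 3/5 of the radiation is given; it should take them off treatment and keep follow-up

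*Combined protocol and SAP*

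**What the plan says.** **The removal rule.** Item 5.6.1 of the combined protocol and SAP applies to patients planned for ICG rather than ALBI. Its verb is mandatory, and the removal is from the study. The trigger and reason are that "they are unable to complete the pre-treatment and post- 3 fraction IC Green tests, as these are necessary for dose adjustment". It does not say what is still followed afterwards, whereas 5.6.4 to 5.6.6 do. ICG is not used for everyone; footnote 6 of table 6.4 limits it: "For patients indicated to receive IC-Green from the treating physician".

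**Replacement.** Under 5.7, patients who lack "IC Green tests or bloodwork to evaluate ALBI score", or the initial 3/5 of treatment, are non-evaluable and are replaced until 80 evaluable patients are reached. Section 11.2 defines evaluable as having received the complete prescribed treatment. It makes allowances where ICG or ALBI results ruled out the second phase and where other toxicity cut treatment short.

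**Follow-up and analysis sets.** Section 5.4 says: "All patients who discontinue treatment should comply with protocol specific follow-up procedures as outlined in Section 6.3". Its exceptions are withdrawn consent, lost capacity to consent, and removal at the investigator's discretion, with a pointer to 5.6. Section 5.5 says: "Patients will be followed for 2 years after completion of treatment or until death, whichever occurs first". Section 7.1.1 makes all patients evaluable for toxicity from the first radiation treatment, and 7.2 analyses safety in everyone who received at least the first part.

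**A parallel case already handled.** If liver function declines and does not recover enough, 5.3 says "then treatment will also be considered complete after 3 fractions". Footnote 5 of table 6.4 then takes the last day of the initial phase as the end of treatment and starts the follow-up calendar.

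**The concern.** A missed pre-treatment ICG test costs little, because no radiation has been given. A missed post-3-fraction test is different: the patient has received 60% of the plan and carries its risk. Not being able to adjust the dose is a sound reason to give no more. It has no bearing on whether the patient's liver function and tumour should still be watched.

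The two criteria in 11.2 for moving to a phase II trial are toxicity (a Child-Pugh rise of 2 points or more within 6 months) in no more than 25% of patients and 1-year local control of at least 80%. Both need outcomes collected after the point at which 5.6.1 removes the patient. If staff apply the item literally, some treated patients have no such outcomes and others take their places. That is selection after treatment has begun, and outcomes not collected cannot be recovered later.

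**Working it through.** **Reading the sections together**

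1. 5.6.1 is mandatory and concerns leaving the study. Items 5.6.3, 5.6.7 and 5.6.8 are permissive, so the difference in verb matters. The sentence introducing the list is itself permissive, which softens it.
2. The discretionary exception in 5.4 refers to 5.6. A mandatory item is not clearly inside that exception, nor clearly outside it.
3. 5.7 can be read two ways. Path by path, an ICG-path patient without the second ICG test is replaced. Read as either test, a patient with ALBI bloodwork stays evaluable. The allowances in 11.2 do not cover a test that was simply missed, which favours replacement.
4. 7.1.1 and 7.2 keep the patient in the safety sets under either reading, but membership does not supply a Child-Pugh score that nobody collected.

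**Size: toxicity**

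The plan's own figure reproduces: 80 × 0.20 = 16 expected events (11.2). The documents give neither the number who would miss the second ICG test (m) nor their toxicity rate (q). Both are assumed here: m = 4 to 8, q = 20% to 60%, with 20% in retained patients.

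- Reading A (replaced, outside the 80): rate in all treated = (16 + m·q)/(80 + m)
- Reading B (inside the 80, outcome missing): rate = (0.2·(80 − m) + m·q)/80

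| q | A, m = 4 | A, m = 8 | B, m = 4 | B, m = 8 |
|---|---|---|---|---|
| 20% | 20.0% | 20.0% | 20.0% | 20.0% |
| 40% | 17.6/84 = 21.0% | 19.2/88 = 21.8% | 16.8/80 = 21.0% | 17.6/80 = 22.0% |
| 60% | 18.4/84 = 21.9% | 20.8/88 = 23.6% | 17.6/80 = 22.0% | 19.2/80 = 24.0% |

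No cell exceeds 25%. At q = 60%, crossing needs 12 patients under A (23.2/92 = 25.2%) or 11 under B (20.4/80 = 25.5%). At q = 40% it needs 27 or 21. As an extreme bound, if every removed patient had toxicity, six would cross under either reading (22/86 = 25.6%; 20.8/80 = 26.0%). For scale, the exact 95% interval for 16/80 is 11.9% to 30.4%.

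**Size: 1-year local control (reading A)**

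Rate = (80·b + m·c)/(80 + m), where b is control in retained patients and c in removed patients. The value b = 97% is the preceding trial's figure in 1.1.4; b = 85% and c are assumed.

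- b = 97%, c = 60%: 80/84 = 95.2% (m = 4), 82.4/88 = 93.6% (m = 8). With c = 0: 92.4%, 88.2%.
- b = 85%, c = 60%: 70.4/84 = 83.8%, 72.8/88 = 82.7%. With c = 0: 81.0%, 77.3%.

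From 85%, falling below 80% takes six removed patients who all fail (68/86 = 79.1%). These are crude proportions. Section 11.3 plans Kaplan-Meier estimates with censoring at the last evaluation, so they show scale only.

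**The case against.** **Silence is common in 5.6, and the general rule fills it.** Items 5.6.2, 5.6.3, 5.6.7 and 5.6.8 also say nothing about later follow-up, and 5.6.5 and 5.6.6 show that being listed in 5.6 need not end observation. If 5.6.1 is mandatory, it falls outside the discretionary exception and 5.4 keeps the patient in follow-up. If it is discretionary, 5.4 permits the exit. A reader might infer that the protocol contradicts itself here; on this argument it does not, and that part stands. What remains is that 5.4 speaks of stopping treatment while 5.6.1 speaks of leaving the study, so staff applying 5.6.1 could reasonably close the patient's follow-up.

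**7.1.1 and 7.2 define who is analysed, and 5.6.1 excludes nobody from those sets.** This also stands. The harm is missing later outcomes, not formal exclusion.

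**ALBI as the substitute.** A reader might infer that a missed ICG test must be replaced by ALBI. Section 1.1.4 says "Thus, either ICG or ALBI can be used in this trial", 5.1.3 and 11.1 accept either for reassessment, and 5.1.1.2 lists "Baseline bloodwork and physical exam to obtain ALBI and Child Pugh score" without limiting it to one path. But the choice can be read as fixed for each patient: 5.1.1.1, footnote 6 of table 6.4 and 5.6.1 itself all fit that reading. No section says a patient may switch mid-course, and the dose-selection toxicity model in 11.1 names only the change in ICGR15. Requiring ALBI would be a clinical dosing decision that the documents do not settle.

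**The numbers are assumed.** They are, and they show how little moves rather than establishing harm.

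**Conclusion.** The point holds as a minor one. As written, 5.6.1 can take a patient off study after 3/5 of the radiation for a reason that supports only withholding the rest, and 5.7 with 11.2 can then replace that patient. This sits poorly with 5.4, 5.5, 7.1.1 and 7.2, but the 5.4 exception and the permissive lead-in to the 5.6 list leave the text ambiguous.

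With 4 to 8 affected patients and toxicity of 20% to 60% among them, both assumed, the toxicity estimate shifts by 0 to 4 points, well inside its sampling error. Two stronger inferences are tempting. One is that toxicity would be understated: that requires patients who miss the test to be sicker, which the documents do not show, and at equal rates only data are lost. The other is that the go decision is at risk: that needs more affected patients, or much worse outcomes among them, than seems likely. Because ICG is used only where the treating physician indicates it, the number affected may be smaller still.

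**What to change.** In 5.6.1, state that a patient who has received any radiation and cannot complete the post-3-fraction ICG test is off treatment, not off study. Follow-up under 6.3 for Child-Pugh score, local control and survival continues, as footnote 5 of table 6.4 already provides for patients who do not qualify for the final phase. The patient stays in the 7.1.1 and 7.2 toxicity and safety analyses even if replaced under 5.7.

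Use the same wording in 5.6.2 for radiation that stops after it has started; that item has the same mandatory verb and the same silence. Leave withdrawal of consent and the discretionary exits (5.4, 5.6.3, 5.6.7, 5.6.8) as they are. Ask the investigators whether ALBI may stand in for a missed mid-treatment ICG test, without making it a required change.

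The cost is a few sentences, a few more patients to track and possibly a slightly higher reported toxicity rate. Under 6.3 the visits follow standard of care, and everything except MRI and ICG may be done by a local physician.
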